7. PLANNED ANALYSIS

For End-Of-Text (EoT) tables, the set of summary statistics is: N / Mean / SD / Min / Median / Max.

For tables that are provided for endpoints with some extreme data, median, quartiles and percentiles should be preferred to mean, standard deviation, minimum and maximum.

For time to event analysis tables, the median and quartiles will be provided.

Tabulations of frequencies for categorical data will include all possible categories and will display the number of observations in a category as well as the percentage (%) relative to the respective treatment group (unless otherwise specified, all patients in the respective patient set whether they have non-missing values or not). Percentages will be rounded to one decimal place. The category missing will be displayed only if there are actually missing values.

All calculated statistics will be presented to one more decimal place than the original measurement accuracy of the variable being summarised.

All p-values will be displayed to four decimal places (or “<0.0001” if appropriate).

7.1 DEMOGRAPHIC AND OTHER BASELINE CHARACTERISTICS

Only descriptive statistics are planned for this section of the report.

The following variables will be displayed in the demographics table: gender, race, age, height, weight, smoking and alcohol status.

Baseline disease status will be summarised descriptively, including the best corrected visual acuity score, intraocular pressure measurement, and the results of the slit lamp examination.

7.2 CONCOMITANT DISEASES AND MEDICATION

Only descriptive statistics are planned for this section of the report.

Concomitant diseases will be coded using the current version of MedDRA coding system. Medications will be coded using the WHO Drug Dictionary (WHO-DD). The coding version number will be displayed as a footnote in the respective output.

The diagnoses and medications will be listed. Subjects without any concomitant diagnosis or therapy should be marked with a “No” in the respective column. Historical anti-DME therapy will be summarised separately according to the ATC4 grouping.

Study eye will be listed.

In addition, any further anti-DME therapy initiated during the course of the trial will be summarised in a separate table along with a summary of reasons for initiating standard of care.

7.3 TREATMENT COMPLIANCE

The percentage of medication taken of study drug as reported on the compliance eCRFs will be summarized descriptively by visit and treatment group. Additionally, summary statistics of overall compliance will be presented by treatment group. Cumulative compliance per patient will be calculated based on weighted average of available on-treatment by visit data, weighted by number of days between visits (e.g., for patient who had 80% compliance at Visit 3 (Week 4, Day 29), 100% compliance at Visit 4 (Week 8, Day 57), 100% compliance at Visit 5 (Week 12, Day 85), the overall compliance would $(29*0.8 + 28*1 + 28*1)/85 = 93.2\%$.

7.4 PRIMARY ENDPOINT

The primary analysis of the primary endpoint, change from baseline in CSFT at 12 weeks, will be performed on the FAS. Therefore, all randomised patients who were treated with at least one dose of BI 1026706/placebo, had a baseline and at least one on-treatment CSFT measurement will be included.

Comparisons between treatment groups for the primary endpoint will be based on a mixed effect repeated measures model (MMRM). This model will include treatment, previous DME treatment, week and treatment by week interaction as fixed categorical effects. Also, baseline CSFT and baseline CSFT by week interaction as continuous fixed effects. An unstructured covariance matrix will be used to model the within-patient variation. The SAS procedure MIXED will be used involving the REML and the Kenward-Roger approximation for the denominator degrees of freedom. This approach is described in Kenward and Roger (R10-4391). Adjusted mean values as well as treatment contrasts will be presented together with the 95% CIs and p-values.

The statistical model will be:

$$\begin{aligned} \text{CSFT change from baseline} = & \text{overall mean} + \text{continuous baseline CSFT} + \\ & \text{previous DME treatment} + \text{treatment} + \text{week} + \\ & \text{baseline CSFT by week interaction} + \\ & \text{treatment by week interaction} + \text{random error} \end{aligned}$$

Baseline CSFT will be defined as the last available CSFT measurement obtained before randomisation.

Data obtained after the start of rescue medication will not be used in the primary analysis of the primary endpoint. Waterfall plots of CSFT change from baseline will be presented. A sensitivity analysis using multiple imputation methods is described in [Section 6.6](#).

[figure not shown]
7.5 SECONDARY ENDPOINTS

7.5.1 Key secondary endpoint

This section is not applicable as no key secondary endpoint has been specified in the protocol.

7.5.2 Other secondary endpoint

Secondary endpoints are safety endpoints. The analyses of safety endpoints are described in [Section 7.8](#).

7.7 EXTENT OF EXPOSURE

Duration of treatment exposure (days) across the randomised treatment period will be calculated for each patient. The total exposure will also be summed over all patients within each treatment group and transformed into patient years. A standard descriptive summary of these data will be provided for the treated set of patients. In addition, the number and percentage of patients in the treatment exposure categories 0-6 weeks, >6 to 12 weeks will be summarised.

Kaplan-Meier curves by treatment group showing the number of patients at risk (exposed) during the randomised treatment period will be produced.

7.8 SAFETY ANALYSIS

All safety analyses will be performed on the treated set and performed in accordance with BI standards. Tabulations of frequencies/proportions will be used for the evaluation of categorical (qualitative) data, and tabulations of descriptive statistics will be used to analyse continuous (quantitative) data.

The format of the listings and tables will follow the BI guideline ‘Reporting of clinical trials and project summaries’ [1, 9]

The individual values of all subjects will be listed, sorted by treatment, subject number and visit. The listings will be contained in Appendix 16.2.

7.8.1 Adverse events

Unless otherwise specified, the analyses of adverse events will be descriptive in nature. All analyses of AEs will be based on the number of patients with AEs and NOT on the number of AEs.

For analysis multiple AE occurrence data on the CRF will be collapsed into an AE provided that all of the following applies:

- All AE attributes are identical (LLT, intensity, action taken, therapy required, seriousness, reason for seriousness, relationship, outcome, AE of special interest).
- The occurrences were time-overlapping or time-adjacent (time-adjacency of 2 occurrences is given if the second occurrence started on the same day or on the day after the end of the first occurrence).

For further details on summarization of AE data, please refer to the guideline ‘Handling and summarization of adverse event data for clinical trial reports and integrated summaries’ [8, 10].

The analysis of adverse events will be based on the concept of treatment emergent adverse events. That means that all adverse events occurring between first drug intake till last drug intake + 4 days will be assigned to the randomised treatment. All adverse events occurring before first drug intake will be assigned to ‘screening’ and all adverse events occurring after the residual effect period will be assigned to ‘post-treatment’ (for selected tables in 16.1.9.2 and listings only). For details on the treatment definition, see [Section 6.1](#).

According to ICH E3 [4], AEs classified as ‘other significant’ needs to be reported and will include those non-serious and non-significant adverse events with
(i) ‘action taken = discontinuation’ or ‘action taken = reduced’, or
(ii) marked haematological and other lab abnormalities or lead to significant concomitant therapy as identified by the Clinical Monitor/Investigator at a Medical Quality Review Meeting.

Adverse events of special interest (AESIs)

The following are considered to be AESIs:

- Hepatic injury defined by the following alterations of hepatic laboratory parameters:
 - Elevation of AST and/or ALT ≥ 3 fold upper limit of normal (ULN) combined with an elevation of total bilirubin ≥ 2 fold ULN measured in the same blood draw sample, and/or
 - Marked peak aminotransferase (ALT, and/or AST) elevations ≥ 10 fold ULN.

Depending on the number of AESIs, either a summary table by MedDRA preferred term or a listing will be produced.

An overall summary of adverse events will be presented. The frequency of patients with adverse events will be summarised by treatment, primary system organ class and preferred term. Separate tables will be provided for patients with other significant adverse events according to ICH E3 [4], for patients with adverse events of special interest and for patients with serious adverse events.

The system organ classes will be sorted alphabetically; preferred terms will be sorted by frequency (within system organ class).

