#### 5.1.2 Secondary Endpoints:

Safety and tolerability of BI 1026706 will be assessed by frequency (in percent) of adverse events over the treatment period.

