#### 5.3.1 Physical examination

A physical examination including height (measured only at Screening), body weight and assessment of the head/neck, skin, upper and lower extremities, thorax, abdomen and nervous system will be carried out by a physician according to the [Flow Chart](#). In addition, further physical examination should be performed if clarification of an AE is necessary. Height/body weight and all clinically significant findings at screening will be documented in the source documents and recorded in the eCRF as baseline conditions.

New findings or worsening of screening conditions at follow-up physical examinations that are, in the opinion of the Investigator, clinically significant or meet other adverse event criteria defined in [Section 5.3.5](#) will be reported as adverse events (AEs).

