#### 7.3.4 Safety analyses

AEs will be coded using the Medical Dictionary for Regulatory Activities (MedDRA) coding dictionary. Standard BI summary tables and listings will be produced. All AEs with an onset between start of treatment and end of the REP (residual effect period), a period of 4 days after the last dose of trial medication, will be assigned to the treatment period for evaluation. All treated patients will be included in the safety analysis. In general, safety analyses will be descriptive in nature and will be based on BI standards. No hypothesis testing is planned.

Statistical analysis and reporting of AEs will concentrate on treatment-emergent AEs. To this end, all AEs occurring between start of treatment and end of the REP will be considered 'treatment-emergent'. The REP is defined as the time period after the last dose administration of trial medication when measurable drug levels or PD effects are still likely to be present. Adverse events that start before first drug intake and deteriorate under treatment will also be considered as 'treatment-emergent'.

Frequency, severity, and causal relationship of AEs will be tabulated by system organ class and preferred term after coding according to the current version of the Medical Dictionary for Drug Regulatory Activities (MedDRA).

Laboratory data will be analysed both quantitatively as well as qualitatively. The latter will be done via comparison of laboratory data to their reference ranges. Values outside the reference range as well as values defined as clinically relevant will be highlighted in the listings.

Clinically relevant ECG findings will be reported as AEs. Quantitative and qualitative ECG data from the ECG reading centre will be reported descriptively.

Treatment groups will be compared descriptively with regard to distribution of parameters as well as with regard to frequency and percentage of patients with abnormal values or clinically relevant abnormal values.

Vital signs, physical examinations, or other safety-relevant data observed at screening, baseline, during the course of the trial and at the end-of-trial evaluation will be assessed with regard to possible changes compared to findings before start of treatment.

[REDACTED]

[REDACTED]

[REDACTED]

[REDACTED]

[REDACTED]

[REDACTED]

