6. GENERAL ANALYSIS DEFINITIONS

6.1 TREATMENTS

For reporting purposes, all randomised patients will be classified into one of the following randomised treatment groups

Sort order	Treatment	Long label	Short label
01	C	BI 1026706 100mg film coated tablets	BI 1026706 100mg
02	D	Placebo matching BI 1026706 100mg film coated tablets	Placebo

These will be the default labels and sort order for reporting the treatment groups.

Patients will be analysed according to the treatment groups to which they were randomised. If there are cases of patients receiving incorrect treatment then an 'as treated' analysis will be performed in addition.

The following treatment periods based on actual start and stop dates of study treatment administration are defined:

Screening: day of informed consent to day prior to the start of randomised study medication

On-treatment: day of first administration of randomised study medication to the last day of study medication administration

Post-treatment: day after the last dose of randomised study medication and thereafter

For the safety analysis, post-treatment events that start up to 4 days after the last administration of trial medication will be assigned to randomised treatment. Adverse events that start on the 5th day after the last administration of trial medication will be considered post-treatment.

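### SAP 7.8.1 assigns every adverse event occurring before first dose to screening, contradicting the protocol rule that such events are treatment-emergent if they deteriorate on treatment

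*SAP*

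**What the plan says.** Protocol 7.3.4 defines treatment-emergent AEs in two parts. The first is a window from start of treatment to the end of the residual effect period, 4 days after the last dose. The second extends it: "Adverse events that start before first drug intake and deteriorate under treatment will also be considered as" treatment-emergent.

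SAP 7.8.1 says it uses the treatment-emergent concept but carries over only the window: "all adverse events occurring between first drug intake till last drug intake + 4 days will be assigned to the randomised treatment". For earlier events it says "All adverse events occurring before first drug intake will be assigned to" screening. It refers to SAP 6.1 for the period definitions. That section gives "Screening: day of informed consent to day prior to the start of randomised study medication" and also has no provision for deterioration. The SAP introduction says the plan is based on protocol Section 7, which contains the omitted sentence.

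The endpoint affected is the one in protocol 5.1.2, the "frequency (in percent) of adverse events over the treatment period". SAP 5.2 lists serious, drug-related and special-interest events under it. Counting is by patient: "All analyses of AEs will be based on the number of patients with AEs and NOT on the number of AEs".

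**The concern.** The protocol lets an event that began before dosing move into the on-treatment count if it gets worse on treatment. The SAP's word All closes that route. An event that began in screening and became severe on treatment, held on a single record with its original start date, would be treatment-emergent under the protocol and a screening event under the SAP.

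AE frequency is the only secondary endpoint named, and evaluating safety and tolerability is part of the primary objective (protocol 2.2). Worsening on drug is among the things those tables should show. Under the SAP rule, whether it appears would depend on how a site happens to record it.

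**Working it through.** The plan states no figure on this point, so there is none to reproduce. The check compares the two texts and then sizes one affected patient.

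**1. The two rules side by side.**

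| Event as recorded | Protocol 7.3.4 | SAP 6.1 and 7.8.1 |
|---|---|---|
| Starts between first intake and last intake + 4 days | treatment-emergent | randomised treatment |
| Starts before first intake, does not deteriorate | not treatment-emergent | screening |
| Starts before first intake, deteriorates, worsening entered as a new record with a post-dose start | treatment-emergent | randomised treatment, through the new record |
| Starts before first intake, deteriorates, one record with the original start | treatment-emergent | screening |

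Only the last row differs. If the SAP rule is applied to original start dates, its set of on-treatment patients is contained in the protocol's set. The SAP count can therefore equal the protocol count or fall below it, but cannot exceed it.

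**2. Can the last row occur?** AEs are collected from informed consent (protocol 5.3.6.2), and screening may last up to 28 days (protocol 6.2.1), so an AE can start before dosing. The exposed group is narrow. Under protocol 5.3.6.1, abnormalities present before trial inclusion are baseline conditions. If one of them worsens, there is no earlier AE record to update. The row is confined to AEs that start between consent and first intake.

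**3. Does any section require a second record?**
- Protocol 5.3.1 has "New findings or worsening of screening conditions at follow-up physical examinations" reported as AEs when clinically significant, and protocol 5.3.6.1 has worsening of pre-existing conditions recorded as an AE. Neither says what start date applies when an AE already on record gets worse.
- Protocol 5.3.6.2 has AEs followed until they resolve or are sufficiently characterised, which is compatible with updating the existing record.
- The collapsing rule in SAP 7.8.1 merges occurrences only when all listed attributes, including intensity, agree. It keeps a separately entered worsening apart but does not tell sites to enter one.

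**4. Size per patient.** Let n be the arm size and k the number of patients in that arm who qualify for a table row only through such an event. The shift in that row is k/n.
- With n = 50 (synopsis): 1/50 = 2.0 percentage points per patient.
- With n = 51 (the 102 in protocol 7.7 divided by 2): 1/51 = 1.96 points.
- For assumed k = 0, 1, 2, 3, 5 and n = 50: 0, 2, 4, 6, 10 points.

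The documents give no rate. If a share q of all patients were affected, the chance of at least one among 100 is 1 − (1 − q)^100. For assumed q = 0, 1%, 2% and 5% this is 0, 0.63, 0.87 and 0.99. These values show only that a small rate would be enough for one case; they are not evidence of a rate.

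The between-arm difference shifts by (k in the active arm − k in the placebo arm)/50, so it can move either way and is unchanged if the two counts are equal.

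**The case against.** The strongest reply is that worsening will normally be a separate record. Protocol 5.3.1 and 5.3.6.1 treat clinically relevant worsening as reportable, and the SAP's collapsing rule expects several occurrences of one event with different intensities. A second occurrence with a post-dose start falls inside the SAP window, and nothing is lost. This is a fair reading of the likely practice, and it stands as a reason not to assert an undercount. It does not remove the conflict, because no supplied section sets the start date. If a new record were always made, the protocol's deterioration sentence would also have little to do.

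A second reply is that the SAP says occurring, not starting, so an ongoing event might be said to occur in both periods. SAP 6.1, however, sorts events at the other end of treatment by when they start, and SAP 7.8.1 gives no rule for an event that spans first intake.

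Third, counting is by patient, so a patient with another on-treatment AE stays in the overall frequency. That is correct, but the patient can still drop out of the preferred-term row.

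Fourth, SAP Section 4 is not in the supplied text and the internal AE guideline cited in 7.8.1 is not available. A declared change in either cannot be excluded. This limits certainty about intent; the wording of 7.8.1 and 6.1 still contradicts protocol 7.3.4.

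Finally, the tables are descriptive, no hypothesis test is planned on safety data, and individual values are listed. All of that stands.

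**Conclusion.** Wrong as written: the SAP rule contradicts the protocol on AEs that start before first intake and deteriorate under treatment.

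A reader might infer that the secondary endpoint will be undercounted, or that several patients per arm will be misclassified. The documents support neither. An undercount needs an AE that starts between consent and first intake, worsens on treatment and has no separate post-dose record, in a patient with no other qualifying AE overall or in that preferred term. No supplied section shows how often this happens.

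The supportable statement is that AE frequency may be undercounted, by 2 percentage points per such patient in an arm of 50, with the number of patients unknown. Nor would the events vanish, since they remain in the listings. The effect is confined to the descriptive safety tables, and the primary analysis of central subfield thickness is untouched.

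**What to change.** In SAP 6.1 and 7.8.1, restore the protocol rule: AEs that start before first intake and deteriorate between first intake and last intake + 4 days are assigned to randomised treatment, and the remaining pre-dose AEs go to screening. So that this can be derived, state that on-treatment worsening is recorded as a separate AE occurrence with its own start date. The protocol does not say which recorded attribute marks deterioration, so the SAP should name the one used.

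The cost is a sentence or two in the SAP, a small derivation and a data-entry clarification to sites. The eCRF is not among the documents. For any record already updated in place, it therefore cannot be told whether the date of worsening was kept, and such records would need a query.

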7.8.2 Laboratory data

The analyses of laboratory data will be descriptive in nature and will be based on BI standards “Handling, Display and Analysis of Laboratory Data” [11]. The following analyses will be presented for all applicable laboratory parameters:

- Descriptive statistics;
- Frequency of patients with possible clinically significant abnormalities.

Baseline is defined by the last available measurement before study drug administration. In case of repeated measurements performed for the same visit the last observation will be used for tabulation.

7.8.3 Vital signs

Only descriptive statistics are planned for this section of the report.

7.8.4 ECG

Clinically relevant ECG findings on-treatment will be reported and summarized as adverse events.

7.8.5 Others

For the clinical trials disclosure process (e.g. clinicaltrial.gov) special safety displays may be necessary, e.g. the number of non-serious Adverse Events. All required displays / ADS for the clinical trials disclosure process will be included in the technical TSAP, section Display Plan or ADS Plan as applicable.

10. HISTORY TABLE

Table 10: 1 History table

Version	Date (DD-MMM-YY)	Author	Sections changed	Brief description of change
Initial	15-AUG-16	[REDACTED]	None	This is the initial TSAP with the necessary information for trial conduct.
Final	25-JUL-17	[REDACTED]	Section 4, [REDACTED] 6.6, [REDACTED] 6.7, 7.3, [REDACTED] 7.7, 7.8.2.	
TSAP Template 001-MCS-40-415_RD-02 (1.0) applied; Section 4, CSET response added; [REDACTED]
 
Section 7.1 and 7.2. Section 6.6, sensitivity analysis described; handling of missing or incomplete AE dates updated; Section 6.7, analyses time windows defined; Section 7.3, treatment compliance defined;
 
[REDACTED]
 
Section 7.7, Kaplan-Meier analyses removed; Section 7.8.2, Analyses of clinical laboratory data specified.

